5.1.3 Dose Limiting Toxicities

For the purpose of guiding decisions regarding dose escalation in Parts 1A, 1B, and 1C, DLTs will be defined based on the incidence, intensity, and duration of AEs excluding toxicities clearly related to disease progression or intercurrent illness. The DLT period will start on the first day of cycle 1 and end at day 28 (therefore, 4 weeks) in Parts 1A, 1B and 1C. The severity of AEs will be graded according to National Cancer Institute (NCI) Common Terminology Criteria for Adverse Events (CTCAE) v5.0.

For the purpose of participant management, DLTs that occur at any time during treatment (not limited to DLT observation period) will result in study drug being held pending evaluation of the event being related to study drug, in accordance with [Section 7.4](#). A participant is considered DLT evaluable if receiving 1 dose of BMS-986315 in Part 1A, 1 dose of BMS-986315 and nivolumab (480mg) in Part 1B, or 1 dose of BMS-986315 and cetuximab (500 mg/m²) in Part 1C, and completing the DLT observation period.

Participants who withdraw from the study during the 4 week DLT evaluation period for reasons other than a DLT may be replaced with a new participant at the same dose level. The incidence of DLT(s) during the 4 week DLT evaluation period will be used in dose escalation decisions and to define the MTD/RP2D in monotherapy and in combination with nivolumab or cetuximab. AEs occurring after the 4-week DLT period will be considered for the purposes of defining the RP2D upon agreement between the Sponsor and Investigators. Participants experiencing a DLT will not be retreated with study drug (except for Grade 3 or 4 acneiform rash in Part 1C), and will enter the safety follow-up period of the study.

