5.1.4 Follow Up

5.1.4.1 Safety Follow-up

Upon completion of study therapy, or once the decision is made to discontinue the participant from treatment, i.e., at end of treatment (EOT), all participants will enter a safety follow-up period.

For participants who complete all scheduled cycles of therapy, the EOT visit will be the same visit as the last scheduled and completed on-treatment visit, and will be the start of the safety follow-up period. For participants who do not complete all scheduled cycles of therapy, the EOT visit will

be the most recent on-treatment visit (with all available safety and response data), and will not need to be repeated. Accordingly, for these participants, this visit will be considered the start of the safety follow-up period.

After the EOT visit, all participants will be evaluated for any new AEs for at least 100 days after the last dose of study treatment. Follow-up visits should occur at Days 30, 60 and 100 (+/- 7 days for all study visits) after the last dose, or the date of discontinuation (+/- 7 days). All participants will be required to complete the 3 clinical safety follow-up visits, regardless of whether new anti-cancer therapy is started, except those participants who withdraw consent for study participation.

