7.4.1 Dose Delays Due to Toxicity

Participants who experience the following must have all study drug(s) withheld:

- Potential DLTs, until DLT relatedness is defined.
- Select AEs and laboratory abnormalities:
 - \geq Grade 1 pneumonitis
 - \geq Grade 2 abnormality in AST, ALT or total bilirubin
 - \geq Grade 2 creatinine increased
 - \geq Grade 2 diarrhea or colitis
 - \geq Grade 2 neurological AE
 - Grade 2 myocarditis
 - AE, laboratory abnormality, or concurrent illness that, in the judgment of the Investigator, warrants delaying study drug administration.
 - For SCCHN participants in Part 1C: Grade 3 or 4 acneiform rash
 - Confirmed SARS-CoV-2 infection

Criteria for participants who are required to permanently discontinue both study drugs is listed in [Section 8](#). Participants not meeting guidelines for permanent discontinuation will be permitted to

resume therapy based on the criteria specified below in [Section 7.4.2](#). Participants eligible to resume study therapy will resume study therapy at the nominal treatment visit following their last received study medication dose.

The end of cycle tumor assessments, such as computed tomography (CT), magnetic resonance imaging (MRI), or positron emission tomography (PET), will continue on a Q8W schedule relative to the participant's first dose, regardless of any treatment delay incurred

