T-HALF _{eff} AUC	Effective elimination half-life that explains the degree of AUC accumulation observed

Individual participant PK parameter values will be derived by non-compartmental methods using a validated PK analysis program. Actual times will be used for all formal analyses.

Sparse nivolumab concentration-time data will be collected and may be used in an integrated PPK or exposure response analysis along with data from other nivolumab studies, which will be the subject of a separate report. Sparse cetuximab concentration-time data will be collected and may be used in an integrated PPK analysis along with data from previous cetuximab monotherapy studies, which will be the subject of a separate report. Separate samples will be collected for PK and IMG assessments.

Table 9.5-3: PK and Immunogenicity Sampling Schedule for Part 1A (CA047-004)

Study Day of Sample Collection ^a (1 Cycle = 4 weeks)	Event	Time Relative to BMS-986315 Dose (hr:min)	BMS-986315 PK Serum Sample	BMS-986315 IMG Serum Sample	ECG ^b
Cycle 1 Day 1	Predose ^c	00:00	X	X	X
	EOI	See note ^d	X		X
		04:00	X		X
Cycle 1 Day 2		24:00	X		
Cycle 1 Day 4 (± 1 Day)		72:00	X		
Cycle 1 Day 8		168:00	X		
Cycle 1 Day 15		336:00	X		
Cycle 1 Day 22		504:00	X		
Cycle 2 Day 1	Predose ^c	00:00	X	X	
	EOI	See note ^d	X		
Cycle 3 Day 1	Predose ^c	00:00	X	X	
	EOI	See note ^d	X		
Cycle 4 Day 1	Predose ^c	00:00	X	X	X
	EOI	See note ^d	X		X
		04:00	X		X
Cycle 4 Day 2		24:00	X		
Cycle 4 Day 4 (± 1 Day)		72:00	X		
Cycle 4 Day 8		168:00	X		

Table 9.5-3: PK and Immunogenicity Sampling Schedule for Part 1A (CA047-004)

Study Day of Sample Collection ^a (1 Cycle = 4 weeks)	Event	Time Relative to BMS-986315 Dose (hr:min)	BMS-986315 PK Serum Sample	BMS-986315 IMG Serum Sample	ECG ^b
Cycle 4 Day 15		336:00	X		
Cycle 4 Day 22		504:00	X		
Cycle 5 Day 1	Predose ^c	00:00	X	X	
Cycle 8 Day 1	Predose ^c	00:00	X	X	
Cycle 12 Day 1	Predose ^c	00:00	X	X	
Cycle 16 Day 1	Predose ^c	00:00	X	X	
Cycle 20 Day 1	Predose ^c	00:00	X	X	
Cycle 26 Day 1	Predose ^c	00:00	X	X	
Follow Up Period					
Follow Up 30 Day			X	X	
Follow Up 100 Day			X	X	

Abbreviations: ECG = electrocardiogram;; EOI = End of infusion; IMG = immunogenicity; PK = pharmacokinetic

^a If a participant permanently discontinues study drug treatment during the sampling period, they will move to sampling at the follow up visits.

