10 STATISTICAL CONSIDERATIONS

10.1 Sample Size Determination

The approximate total number of participants treated will be up to 308 for Part 1 as shown below:

- In Part 1A, approximately 36 participants will be treated in dose escalation phase, and up to 40 participants will be treated in SCCHN PD cohort, for a total of up to approximately $36+40=76$ participants.
- In Part 1B, with 2 SCCHN PD cohorts, up to approximately $36+40+40=116$ participants will be treated, with 36 participants in dose escalation phase, and 40 participants in each SCCHN PD cohort.
- In Part 1C, similar to part 1B, up to approximately $36+40+40=116$ participants will be treated.

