10.2 Populations for Analyses

For purposes of analysis, the following populations are defined in Table 10.2-1 below:

Table 10.2-1: Populations for Analysis	
Population	Description
All Enrolled	All participants who signed an ICF and were registered into the IRT.
All Treated	All enrolled participants who receive at least 1 dose of study drug.

Table 10.2-1: Populations for Analysis

Population	Description
Response-evaluable	All treated participants with measurable disease at baseline and 1 of the following: (a) at least 1 post baseline tumor assessment, (b) radiologic progression, (c) death.
PK	All treated participants that have available serum concentration data that allow for computation of PK parameter values.
Immunogenicity	All Treated participants with baseline and at least 1 pre-infusion immunogenicity assessment.
Biomarker	All Treated participants who have available biomarker data.

Abbreviations: ICF = informed consent form; IRT = Interactive Response Technology; PK = pharmacokinetics.

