10.3.4 Immunogenicity Analyses

Endpoint	Statistical Analysis Methods

 Incidence of anti-drug antibodies to BMS-986315 Incidence of anti-drug antibodies to nivolumab, with combination treatment Incidence of anti-drug antibodies to cetuximab with combination treatment 
Baseline anti-drug antibody-positive participant is defined as a participant who has an anti-drug antibody-detected sample at baseline^a anti-drug antibody-positive participant is a participant with at least 1 anti-drug antibody-positive sample relative to baseline after initiation of the treatment.
	
Frequency distribution baseline anti-drug antibody-positive participants and anti-drug antibody-positive participants after initiation of the monotherapy and combination treatment.
 
Frequency distribution of nivolumab baseline anti-drug antibody-positive participants and anti-drug antibody-positive participants after initiation of the combination treatment.
 
Frequency distribution of cetuximab baseline anti-drug antibody-positive participants and anti-drug antibody-positive participants after initiation of the combination treatment.

^a Baseline sample is the last sample before initiation of the treatment

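### The Immunogenicity population, naturally read, excludes participants who stop after one dose even when their scheduled follow-up ADA samples were collected

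*Combined protocol and SAP*

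**What the plan says.** Table 10.2-1 (section 10.2) defines the Immunogenicity population as "All Treated participants with baseline and at least 1 pre-infusion immunogenicity assessment". Footnote a of section 10.3.4 fixes baseline: "Baseline sample is the last sample before initiation of the treatment". The same section calls a participant ADA-positive on the strength of at least one positive "sample relative to baseline after initiation of the treatment". That definition is not limited to samples taken before an infusion.

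The sampling schedules (Tables 9.5-3 to 9.5-5) carry a common footnote: "If a participant permanently discontinues study drug treatment during the sampling period, they will move to sampling at the follow up visits". Immunogenicity samples are scheduled at the Day 30 and Day 100 follow-up visits in all three parts. Section 5.1.4.1 adds "All participants will be required to complete the 3 clinical safety follow-up visits", apart from those who withdraw consent. Section 5.1.3 says "Participants experiencing a DLT will not be retreated with study drug", with an exception for Grade 3 or 4 acneiform rash in Part 1C.

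**The concern.** The population row and the ADA-positive definition do not cover the same participants. Section 10.3.4 accepts any sample after treatment starts, while the population row asks for a pre-infusion sample. A follow-up sample precedes no infusion, so it can make a participant positive but cannot bring that participant into the set.

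This affects participants who receive one dose and are then sampled only at follow-up. They stop for reasons such as a DLT or early progression, so they are a selected group. The endpoint at stake is the incidence of antibodies to BMS-986315, a secondary endpoint in Table 4-1. The same row would govern the exploratory nivolumab and cetuximab antibody summaries.

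**Working it through.** The plan states no figure that depends on this definition, so there is nothing to reproduce. The check sets the schedule beside the definitions.

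**Step 1. Scheduled immunogenicity samples (Tables 9.5-3, 9.5-4, 9.5-5; the same time points in each part).**

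| Sample | Position | Precedes an infusion | Can count towards ADA-positive (10.3.4) |
|---|---|---|---|
| Cycle 1 Day 1 predose | Baseline; the only scheduled pre-treatment sample | Yes | No |
| Day 1 predose of Cycles 2, 3, 4, 5, 8, 12, 16, 20, 26 | Post-baseline | Yes | Yes |
| Follow-up Day 30 and Day 100 | Post-baseline | No | Yes |

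The first post-baseline sample that is also pre-infusion is therefore Cycle 2 Day 1. In Part 1C the Day 15 cetuximab infusion does not change this, because no immunogenicity sample is scheduled that day.

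**Step 2. Who is in the set.**

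| Samples available | Natural reading of the row | Proposed wording | Can be ADA-positive under 10.3.4 |
|---|---|---|---|
| Baseline and a later predose sample | In | In | Yes |
| Baseline and follow-up only (one dose given) | Out | In | Yes |
| Baseline only | Out | Out | No |

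The second line is the gap. Someone who had several doses and first turns positive at Day 100 counts as positive. Someone who had one dose and turns positive at Day 100 is not in the set.

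**Step 3. Who stops after one dose.** Section 5.1.3 bars retreatment after a DLT, and the DLT window is the first 28 days. Sections 5.1.2.1 to 5.1.2.3 allow an extra participant per cohort because some will discontinue inside that window, with disease progression as the example. Not every cycle 1 DLT leads to exclusion. Section 7.4.1 withholds drug for "Potential DLTs, until DLT relatedness is defined", so a Cycle 2 Day 1 predose sample may already have been drawn. In Part 1C, some participants may also continue BMS-986315 after a cetuximab infusion reaction or rash (sections 7.4.2.1 and 7.4.2.3). Hence most, not all.

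**Step 4. Effect on the reported incidence.** Let n1 be the participants with a later predose sample and p1 their ADA incidence. Let n2 be those with follow-up samples only and p2 theirs.

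- Natural reading: incidence = p1.
- All assessed participants: incidence = (n1·p1 + n2·p2) / (n1 + n2) = p1 + w·(p2 − p1), where w = n2 / (n1 + n2).
- Difference: w·(p2 − p1).

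The documents give neither w nor p2 − p1. The difference is zero if n2 = 0 or p2 = p1, and otherwise can take either sign.

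**The case against.** **A later SAP may settle it.** Section 10.3 leaves participant selection to a SAP finalized before database lock, and section 10.3.4 names no denominator. Both points stand, so the link from this row to the ADA incidence is an inference. But the protocol already defines the population, nothing in the document reviewed corrects it, and a SAP that repeats the row would carry the gap forward.

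**No decision rests on it.** This stands. No test or escalation rule uses ADA incidence, and section 10.3.8 plans no formal inference requiring adjustment.

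**Some excluded participants would be lost anyway.** This also stands. Those who die, withdraw consent or are lost before giving a follow-up sample stay out under any sensible wording. Only one-dose participants who do give a follow-up sample are affected.

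**Stronger readings that a reader might infer.** First, the row might seem to admit participants with no post-baseline result, because the Cycle 1 Day 1 sample is both baseline and pre-infusion. The words do allow it: the Response-evaluable row of the same table asks for a post-baseline assessment and this row does not. But that reading leaves the second condition with no work to do, and an analyst is unlikely to adopt it. It is a secondary drafting point.

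Second, one might size the loss from the simulated DLT rates in Appendix 8, Table 2. Every scenario there contains a dose with a 30% DLT rate. These are design scenarios, not forecasts, and they count DLTs rather than one-dose participants who also gave a follow-up sample.

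**Conclusion.** The point holds as a minor defect in a population definition. Followed as naturally read, the row discards scheduled and collected post-dose ADA results from one-dose participants, who are not a random subset, and it does not match the ADA-positive definition in section 10.3.4.

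The conclusion rests on two assumptions: that the pre-infusion sample is meant to follow baseline, and that this set is the denominator for ADA incidence. The consequence is limited to the reporting of descriptive immunogenicity endpoints. The documents do not support a claim that ADA incidence will be under- or over-stated, because the share affected and its ADA rate relative to the rest are both unknown. Nor do they support any effect on dose escalation or on the primary safety objective.

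**What to change.** In Table 10.2-1, replace the pre-infusion requirement with at least one post-baseline immunogenicity assessment, predose or follow-up, for the relevant drug, and keep the baseline requirement. This also closes the literal reading, and it covers a participant whose Cycle 2 Day 1 predose sample was drawn but who was then not dosed.

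In section 10.3.4, name two denominators:

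- for ADA-positive after the start of treatment, the revised Immunogenicity population;
- for baseline ADA-positive, treated participants with a baseline sample, since no later sample is needed and a single post-baseline set would drop valid baseline results.

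Carry both into the SAP before database lock. The cost is a few words in Table 10.2-1, section 10.3.4 and the SAP. No new samples, visits or assays are needed.

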10.3 Statistical Analyses

The statistical analysis plan will be developed and finalized before database lock and will describe the selection of participants to be included in the analyses, and procedures for accounting for missing, unused, and spurious data. Below is a summary of planned statistical analyses of the primary and secondary endpoints.

A description of the participant population will be included in a statistical output report, including subgroups of age, gender and race.

10.3.1 Efficacy Analyses

The main efficacy analyses (Table 10.3.1-1) will be performed on the treated population, presented separately by study part. Efficacy analyses based on the response-evaluable population may be performed for interim analyses when the minimum follow-up period is less than sufficient to warrant adequate interpretation of the result.

Table 10.3.1-1: Efficacy Statistical Analysis

Endpoint	Statistical Analysis Methods
ORR is defined as the proportion of population of interest whose BOR is either CR or PR per RECIST v1.1 BOR for a population of participants will be assessed per RECIST v1.1.	Estimate of ORR and corresponding 2-sided exact 95% CI using the Clopper-Pearson method by treatment for each tumor type
Median DOR DOR for a participant with a BOR of CR or PR is defined as the time between the date of first response and the date of the first objectively documented tumor progression per RECIST v1.1 or death, whichever occurs first.	Median duration of response using the Kaplan-Meier method and corresponding 2-sided 95% CI using Brookmeyer and Crowley methodology (using log-log transformation) by treatment for each tumor type Analysis is dependent on the number of responders
PFSR at 6, 9, and 12 months PFS for a participant is defined as the time from the first dosing date to the date of first objectively documented disease progression or death due to any cause, whichever occurs first.	Estimate by the Kaplan-Meier method and corresponding 95% CI will be derived based on Greenwood formula by treatment for each tumor type.

Abbreviations: BOR, best overall response; CI, confidence interval; CR, complete response; DOR, duration of response; ORR, overall response rate; PFS, progression free survival; PFSR, progression free survival rate; PR partial response; RECIST, Response Evaluation Criteria In Solid Tumors

Overall survival rate (OSR) at 1 year and 2 years will be analyzed similarly to PFSR. Details of the censoring scheme on time-to-event endpoints such as DOR, PFS, and OSR will be described in the Statistical Analysis Plan.

10.3.2 Safety Analyses

All safety analyses will be performed on the treated population. Statistical analyses for Safety are shown in Table 10.3.2-1.

Table 10.3.2-1: Safety Statistical Analysis	
Endpoint	Statistical Analysis Methods
Incidence of AEs, SAEs, AEs meeting protocol defined DLT criteria, AEs leading to discontinuation, and death; AEs will be graded according to CTCAE v5.0.	DLT rate by dose level, frequency distribution of treated participants with AE using the worst CTC grade. Participants will only be counted (1) once at the PT level, (2) once at the system organ class level, and (3) once in the 'total participant' row at their worst CTC grade, regardless of system organ class or PT.
Laboratory abnormalities Laboratory values will be graded according to CTCAE v5.0.	Laboratory shift table using the worst CTC grade on treatment per participant

Abbreviations: AE, adverse event; CTC, common terminology criteria; CTCAE, common terminology criteria for adverse events; DLTs, dose-limiting toxicities; PT, preferred term; SAE, serious adverse event.

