5.1.2.1 BMS-986315 Monotherapy Dose Escalation Design (Part 1A)

Approximately 36 participants are expected to be treated during the BMS-986315 Monotherapy Dose Escalation (Part 1A) of the study guided by TITE-BOIN design ([Figure 5.1.2.1-1](#), TITE BOIN [Appendix 8](#)) for the primary objective. Additionally, up to approximately 40 participants are expected to be treated in the SCCHN PD cohort in monotherapy (in order to have 30 evaluable).

[figure not shown]
In dose escalation, each participant will be administered IV doses of BMS-986315 in planned dose levels of 80 mg followed by 200 mg, 600 mg, 1200 mg, and 2400 mg Q4W once per cycle, for up to 26 cycles (104 weeks) of study therapy, unless criteria for study drug discontinuation are met earlier (see [Section 8](#)).

Prior to declaring the MTD, and in consultation with investigators, the Sponsor has the option to investigate dose levels intermediate to those defined in the protocol. Planned dose levels may be modified based upon the DLT data in the evaluated doses and clinical evaluation of all available safety and PK/pharmacodynamic data. Once the tolerability (during the DLT evaluation) of a dose level has been established, additional participants may be added at that dose level to better characterize the safety, PK, and pharmacodynamic profiles.

The BMS-986315 Monotherapy Dose Escalation (Part 1A) phase of the study will evaluate the safety and tolerability of BMS-986315, based on DLTs, guided by the TITE-BOIN design. During the monotherapy dose escalation phase, approximately 3 participants will be treated at each dose level, allowing at least 2 participants for a decision at the lower dose levels. In order to allow for any unforeseen discontinuations (such as disease progression) before the 4-week DLT period (28 days) is completed, an extra participant may be enrolled in each dose escalation cohort after the 2 initial dose levels. Therefore, there may be a total of 4 participants (3 + 1) at the start of a cohort. Cohort tolerability assessment and subsequent dose recommendation will occur when at least 2 out of 3 or 3 out of 4 participants within a cohort have completed the 4-week (28 day) DLT period or have been followed sufficiently based on the TITE-BOIN design to make an escalation decision. Any toxicities that occur beyond the DLT period will be considered in making dose level decisions and/or dose level modifications. Additional information on DLTs can be found in [Section 5.1.3](#).

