5.1.3.1 Hepatic Dose Limiting Toxicity

Any 1 of the following events, excluding toxicities clearly related to disease progression or intercurrent illness, will be considered a hepatic DLT:

- Grade 4 elevations in serum transaminases (AST, ALT), alkaline phosphatase (ALP) or total bilirubin, in the absence of cholestasis.
- Grade 3 elevations in serum transaminases (AST, ALT) or alkaline phosphatase (ALP) in the absence of cholestasis, lasting longer than 5 days.
- Grade 2 elevations in AST or ALT with symptomatic liver inflammation (e.g., right upper quadrant tenderness, jaundice, and pruritus).
- AST or ALT $> 3 \times$ ULN and concurrent total bilirubin $> 2 \times$ ULN without initial findings of cholestasis (elevated ALP, eg, findings consistent with Hy's law or FDA definition of potential drug-induced liver injury [pDILI]). Note that this specific category of DLT uses ULN rather than CTCAE grade for definition.

5.1.3.2 *Hematologic Dose Limiting Toxicity*

Any of the following events will be considered a DLT:

- Grade 4 neutropenia
- Grade 4 thrombocytopenia
- Grade 4 anemia
- Grade 3 thrombocytopenia with clinically significant bleeding, or any requirement for platelet transfusion.
- Febrile neutropenia
- Grade ≥ 3 hemolysis (i.e., requiring transfusion or medical intervention such as steroids).

5.1.3.3 *Dermatologic Dose Limiting Toxicity*

Any of the following events will be considered a DLT:

- Grade 4 skin toxicity of any duration
- Grade 4 rash
- Grade 3 rash if no improvement (i.e., resolution to \leq Grade 2) after a 1 to 2 week infusion delay. Topical steroid treatment is allowed for symptom control.

5.1.3.4 *Other Dose Limiting Toxicities*

Any of the following events will be considered a DLT:

- Grade 2 drug-related uveitis, episcleritis, iritis eye pain or blurred vision that does not respond to topical therapy and does not improve to Grade 1 severity within 2 weeks OR requires systemic treatment.
- Grade 2 pneumonitis that does not respond to dose delay and systemic steroids within 14 days.
- Grade ≥ 3 drug-related uveitis, episcleritis, iritis, pneumonitis, bronchospasm or neurologic toxicity.
- Grade 4 hypersensitivity/infusion reaction, or Grade 3 that does not resolve to Grade 1 in < 6 hours.

- Grade 4 colitis
- Grade 3 colitis that does not respond within 48 hours of systemic steroid treatment.
- Any death not clearly due to the underlying disease or extraneous causes.

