Cetuximab is known to cause serious and fatal infusion reactions. Among 1373 patients who received cetuximab across clinical trials, any grade infusion-related reactions (IRR) occurred in 8.4% and Grade 3/4 in 2.2% of patients.²² IRRs might manifest with fever, chills, rigors, headache, rash, pruritus, arthralgia, hypotension, hypertension, bronchospasm, rapid onset of airway obstruction, shock, loss of consciousness, myocardial infarctions and/or cardiac arrest. Approximately 90% of severe IRR to cetuximab occur in the first infusion despite premedication with antihistamines. Infusions should be performed in a setting with resuscitation equipment and other agents necessary to treat anaphylaxis.

All Grade 3 or 4 infusion reactions should be reported within 24 hours to the study medical monitor or designee and reported as an SAE if it meets the criteria. Infusion reactions should be graded according to NCI CTCAE (Version 5.0) guidelines. All Grade 3 or 4 infusion reactions to cetuximab will be considered as DLT and will incur in immediate discontinuation of cetuximab treatment. Participants may continue to receive treatment with BMS-986315 upon discussion between investigator and the Sponsor.

Treatment recommendations are provided below and may be modified based on local treatment standards and guidelines, as appropriate.

For treatment with cetuximab, all recommendations described in [Section 7.4.2.2](#) apply. In addition:

- Premedicate with a histamine-1 (H1) receptor antagonist intravenously 30–60 minutes prior to the first dose or subsequent doses as deemed necessary
- For Grade 1 or 2 infusion reactions: interrupt the infusion and upon recovery, resume the infusion at 50% of the infusion rate.
- For Grade 3 or 4 infusion reactions: immediately and permanently discontinue cetuximab.

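### The by-dose DLT rate uses all treated participants, so early non-DLT losses count as DLT-free; the DLT-evaluable definition is unused and misdrafted, and Appendix 8 does not place such losses

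*Combined protocol and SAP*

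**What the plan says.** **Reporting.** Section 10.3.2: "All safety analyses will be performed on the treated population". Table 10.3.2-1 places the DLT rate for each dose under that rule, and Table 4-1 makes DLTs part of the primary endpoint. Table 10.2-1 defines All Treated as "All enrolled participants who receive at least 1 dose of study drug" and has no DLT-evaluable set. Section 10.3 says that a later SAP, due before database lock, "will describe the selection of participants to be included in the analyses".

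**Definition.** Section 5.1.3 calls a participant DLT evaluable after one dose of the assigned drug or drugs plus completion of the window; the sentence ends "in Part 1C, and completing the DLT observation period". It has no alternative for someone who had a DLT. People who withdraw within the four weeks "for reasons other than a DLT may be replaced with a new participant at the same dose level". Section 5.1.3.4 lists as a DLT "Any death not clearly due to the underlying disease or extraneous causes". For Part 1C, Section 7.4.2.3 adds: "All Grade 3 or 4 infusion reactions to cetuximab will be considered as DLT and will incur in immediate discontinuation of cetuximab treatment".

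**Escalation.** Figure 5.1.2.1-1 and Appendix 8 Table 1 work from patients treated, patients with a DLT and patients pending. A patient lost without a DLT has no stated category, although Section 5.1.2.1 foresees such losses: to allow for "any unforeseen discontinuations (such as disease progression) before the 4-week DLT period (28 days) is completed, an extra participant may be enrolled" after the two lowest levels. Sections 5.1.2.2 and 5.1.2.3 have the same provision.

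**The concern.** Time that nobody observed is counted as time without a DLT, so the reported rate is biased downward. The definition that could prevent this is left out of the analysis sections. As worded it also could not be adopted, because it would drop some of the clearest DLTs.

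The same gap reaches dose decisions. A lost participant can be read as complete, pending or removed, and Table 1 can give different answers. Those decisions are made long before an SAP that is due only by database lock. Replacement does not settle the matter: it is optional, and it adds a participant without removing the lost one from the treated count.

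**Working it through.** **1. Reproducing the plan's figures.** Inputs: target 0.30 (10.1.1, Appendix 8), with the usual BOIN values 0.6 × 0.30 = 0.18 and 1.4 × 0.30 = 0.42.
- Escalation: ln(0.82/0.70) / ln[(0.30 × 0.82)/(0.18 × 0.70)] = 0.2365 (plan: 23.6%).
- De-escalation: ln(0.70/0.58) / ln[(0.42 × 0.70)/(0.30 × 0.58)] = 0.3585 (plan: 35.9%).
- STFT cut-off for n treated, r DLTs, c pending: c − (nλ − r)/[p/(1−p)], with p = (r + 0.15)/(n − c + 1). For 5/1/1: p = 1.15/5 = 0.23, odds 0.2987, so 1 − (5 × 0.2365 − 1)/0.2987 = 0.389 (Table 1: 0.39). All 25 cut-offs checked agree to rounding.

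**2. Reported rate.** Let p = 0.30 be the true rate and w the assumed proportion lost. DLT and exit times are independent and uniform over 28 days.
- All treated: p(1 − w/2).
- Completers plus anyone with a DLT: p(1 − w/2) / [1 − w(1 − p/2)].
- Follow-up-weighted: each loss counts for the fraction of the window observed. The mean unobserved fraction among those assumed to leave is 1/2 − p/6 = 0.45, so the rate is p(1 − w/2)/(1 − 0.45w).

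| w | All treated | Evaluable | Follow-up-weighted |
|---|---|---|---|
| 5% | 0.2925 | 0.2925/0.9575 = 30.5% | 0.2925/0.9775 = 29.9% |
| 10% | 0.285 | 0.285/0.915 = 31.1% | 0.285/0.955 = 29.8% |
| 20% | 0.270 | 0.270/0.830 = 32.5% | 0.270/0.910 = 29.7% |

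If every loss falls in week 1, the mean exit is at one eighth of the window and the all-treated rate is p(1 − 0.875w): 28.7%, 27.4% and 24.8%.

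**3. Table 1.** I compared r DLTs in n with r in n+1, no one pending, so that the extra patient is a loss entered as completed. Of the 117 cells with 3 to 15 treated and at least one patient without a DLT, 13 relax and none tightens. Eight change escalate/stay/de-escalate. Each has a printed one-pending cut-off, so carrying the loss through STFT gives the stricter decision for an early exit:

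| Without the loss | Entered as completed | Cut-off | Day (× 28) |
|---|---|---|---|
| 1/2 De-escalate | 1/3 Stay | 0.88 | 24.6 |
| 1/4 Stay | 1/5 Escalate | 0.39 | 10.9 |
| 2/5 De-escalate | 2/6 Stay | 0.73 | 20.4 |
| 2/8 Stay | 2/9 Escalate | 0.59 | 16.5 |
| 3/8 De-escalate | 3/9 Stay | 0.58 | 16.2 |
| 4/11 De-escalate | 4/12 Stay | 0.43 | 12.0 |
| 3/12 Stay | 3/13 Escalate | 0.77 | 21.6 |
| 5/13 De-escalate | 5/14 Stay | 0.97 | 27.2 |

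Example: five treated, one DLT, three completers and one loss on Day 7 (7/28 = 0.25). Entered as completed: Escalate. Carried, 0.25 < 0.39: Stay. Removed (4/1): Stay.

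The other five reverse elimination, with de-escalation either way: 3/4 to 3/5, 4/6 to 4/7, 5/9 to 5/10, 6/11 to 6/12, 7/13 to 7/14.

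**4. Simulation, relative only.** 20,000 trials per cell, Table 2 scenarios. The no-loss baseline does not reproduce Table 2 (Scenario 4 correct selection 65.2% against 71.2%), so only differences from that baseline are used. Change in selection above the true MTD, Scenarios 1 to 3, in points:

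| Handling | 10% lost | 20% lost |
|---|---|---|
| Counted as completed | +0.6 to +1.5 | +2.8 to +4.9 |
| Carried through STFT | −0.5 to −1.8 | −0.6 to −3.2 |
| Removed | −2.1 to −3.5 | −4.1 to −6.6 |

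**The case against.** The best reply is that little is lost in practice. BMS-986315 and nivolumab are given once in the window, on Day 1. Sections 5.1.4.1 and 8.2 keep people who stop treatment under follow-up, so real losses come mainly from death from disease, withdrawn consent or loss of contact. At 5% the bias is under one point with uniform timing, and a separate run of 8,000 trials per cell moved selection above the MTD by only +0.9, 0.0 and −0.3 points. One participant among 12 at a dose is worth 8.3 points. TITE-BOIN only guides the decision, alongside clinical review. All of this stands and limits the size of the point. The SAP deferral does not remove it: 10.3.2 already names the population, and escalation comes first.

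Three stronger readings are tempting and are not supported.
- A reader might infer that Appendix 8 requires a loss to be entered as fully observed. It does not classify the case at all. Section 5.1.3 makes that person non-evaluable, and Parts 1B and 1C time decisions on three evaluable participants.
- A reader might infer that fatal DLTs are actually dropped. Table 1 and 10.3.2 both count treated patients, and the replacement wording in 5.1.3 shows that participants with a DLT were meant to be kept. This is a drafting error.
- A reader might infer that 5.1.3 and 7.2 conflict on replacement. Both can be followed; a cross-reference is editorial.

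**Conclusion.** The point holds as a should-fix matter of definition and reporting. As written, the by-dose DLT rate treats unobserved time as DLT-free. The bias is about 0.8, 1.5 and 3.0 points at a true 30% for losses of 5%, 10% and 20% with uniform timing, and larger if losses come early. These loss rates are assumptions and may be high. The evaluable definition needs an alternative for participants who had a DLT before it can be used.

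For escalation the finding is an omission whose most permissive reading relaxes 13 cells, not a rule that is known to be applied. Carrying the loss keeps the DLT rate close to unbiased (29.8% and 29.7% at 10% and 20%). At 10% it moves selection above the MTD by about as much as counting everyone, but downward. Removing losses from running decisions moves selection furthest from the no-loss case and is not recommended.

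**What to change.** 1. Correct 5.1.3 and add a DLT-evaluable set to Table 10.2-1: escalation participants with a protocol-defined DLT in Days 1 to 28 (including one that prevents completion of the Cycle 1 dose), or who received the required Cycle 1 dose or doses and were followed through Day 28 without one.
2. In Table 10.3.2-1, report the DLT rate for each dose on that set with the all-treated rate alongside. Note that the first runs slightly high and the second low. Keep every other safety table on All Treated.
3. State in Appendix 8 that a participant lost before Day 28 without a DLT is carried with actual follow-up through STFT, not entered as completed. Apply the same rule in the final isotonic estimate. Say that this person does not count toward the suspension rule for more than 50% pending, because the data will never mature. Where a printed row reads Suspend only because of a carried loss, the cut-off comes from the same formula.
4. As an editorial matter, cross-refer the replacement wording in 5.1.3 and 7.2.

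The cost is wording; no new data are needed, and the boundaries and printed Table 1 rows are unchanged. There are two limits. Elimination in Table 1 depends on the treated count, so carrying leaves the five elimination cells as they are. Carrying also lowered correct selection in Scenario 4 against the no-loss run, by 0.7 to 1.6 points at 10% and 3.0 to 8.1 at 20%.
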